2.9 Safety analyses

Safety analyses will be conducted on data from the Extension Safety Set by initial treatment received in the Core study. Adverse events, vital signs, health status and laboratory evaluations will be summarized and listed.

The safety observation period (days) for treated patients comprises two segments:

[figure not shown]
- (1) the first segment starts from first study treatment in the Core study and ends at the last visit in the Core study. This corresponds to period "a" in [Figure 2-1](#).
- (2) the second segment starts from the Extension baseline visit to the last visit in the Extension study. This corresponds to period "c" in [Figure 2-1](#).

This safety observation period for a patient can be seamless (when the last visit of Core study occurs on the same day as the Extension baseline visit) or non-seamless (when the last visit of Core study does not occur on the same day as the Extension baseline visit). Any safety signs occurring in the gap, segment "b", will be reported as medical history of Extension baseline as in [Section 2.3](#). The resulted safety observation period (days) for the Extension study is defined as below:

- For seamless roll-over:
 - Safety observation period for the Extension: date of last visit in Extension study – date of baseline visit of Extension study
 - Safety observation period from Core baseline: date of last visit in Extension study – date of first study treatment in Core study + 1
- For non-seamless roll-over:

- Safety observation period for the Extension: date of last visit in Extension study (or cut-off date) – date of baseline visit of Extension study +1
- Safety observation period from Core baseline: (date of last visit in Extension study – date of baseline visit of Extension study +1) + (date of last visit in Core study – date of first study treatment in Core study +1)

Figure 2-1 Safety observation period

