1.2 Study objectives and endpoints

[figure not shown]
All study objectives will be assessed by initial study treatment received at baseline of the Core study CRFB002H2301. The objectives, along with its endpoints and time point for analyses are presented in [Table 1-1](#).

[figure not shown]
Table 1-1 Study objectives and endpoints

OBJECTIVE	Endpoint Title, Description and Reporting Time frame for analysis and Unit of measure
Primary	
To evaluate the visual function of patients, by assessing the visual acuity in the better-seeing eye at the patient's fifth birthday ^{a,e}	Title: visual acuity in the better-seeing eye at the patient's fifth birthday Unit of measure: visual acuity score (Lea symbols optotypes) Time frame: at the patient's fifth birthday ^e
Secondary	
To evaluate the safety outcomes by analyzing the type, frequency and severity of ocular and non-ocular Adverse Events ^b	Title: ocular and non-ocular Adverse Events Unit of measure: number and percentage of patients having e.g. any AE; number of hospitalization/ prolongation of hospitalization due to SAE Time frame: from the first study treatment in the Core study up to V203 (Week 40), V302 (the patient's 2 years' corrected age) and V399 (the patient's fifth birthday) in the Extension study

OBJECTIVE	Endpoint Title, Description and Reporting Time frame for analysis and Unit of measure
To evaluate the visual function by assessing the visual acuity in the worse-seeing eye at the patient's fifth birthday ^a	
Title: visual acuity in the worse-seeing eye at the patient's fifth birthday
 
Unit of measure: visual acuity score (Lea symbols optotypes)
 
Time frame: at the patient's fifth birthday

To evaluate the absence of active ROP at 40 weeks and 52 weeks post baseline visit in the Core study	
Title: absence of active ROP
 
Unit of measure: number and percentage of patients
 
Time frame: at V203 and V301 (40 weeks and 52 weeks post baseline visit in the Core study)

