- Adverse Events (AEs) and Serious Adverse Events (SAEs) which started after end of Core study and resolved before the time of Extension study enrollment (Baseline Visit) will be reported as Extension medical history with medical history ongoing status as “No”.
- Adverse Events (AEs) and Serious Adverse Events (SAEs) which started after end of Core study and are ongoing at the time of Extension study enrollment (Baseline Visit) will be reported as Extension medical history with medical history ongoing status as “Yes”..

Tabular format for Data Entry rules in the Extension study eCRF for Medical History

Item	Started	Ended	Action for ECRF
Med Hx	before Core	Ongoing end of Core and at beginning of Ext	Don't record as MHx in Ext (MHx of Core)
Med Hx	before Core	Ongoing end of Core and finished in Gap	Don't record as MHx in Ext (MHx of Core)
Med Hx	Gap	Gap	Record as MHx in Extension (not ongoing)
Med Hx	Gap	Ongoing at beginning of Ext	Record as MHx in Extension (ongoing)
(S)AEs	Core	ongoing end of Core and finish in gap (before Ext)	Record as MHx in Extension (not ongoing)
condition	Gap	Ongoing at beginning of Ext	Record as MHx in Extension (ongoing)
condition	Gap	Gap	Record as MHx in Extension (not ongoing)

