2.5.3 Surgical and medical procedure

Surgical and medical procedures will be displayed separately for Core and Extension studies, and separate from concomitant medications.

Guidance of Data Entry rules in the Extension study eCRF which provides details on handling of Surgeries and procedures in Extension study:

- It is not expected that records for surgery and procedures in the Core study must be re-entered in the Extension study, as they are usually not continuing over a long period of time. However, if any, records are expected to match (with the exceptions of end dates).
- Procedures which occurred after end of Core study and ended prior to enrollment in to the Extension study should be entered in Extension medical history.

The same approach will be taken to display surgeries and procedures as specified for concomitant medications in [Section 2.5.2](#). Surgical and medical procedures will be identified by primary system organ class and preferred term according to the WHO Drug Reference List dictionary.

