2.9.2 Adverse events (AEs)

As a default, no summary tables for AEs that occur prior to the first study treatment in either eye will be produced.

Adverse events that occur prior to the first study treatment in either eye in Core study will be listed for patients.

Adverse events will be deemed treatment emergent if the AE start time is on or after the time of dose of the first study treatment in the Core study. When an AE's start date is equal to the date of first study treatment and either the start time of the AE or the first treatment time is missing, AEs are defined as treatment emergent. As stated in [Appendix 4](#), adverse events with completely missing start date will be defined as treatment emergent.

The AE incidence rates will be tabulated using the latest MedDRA SOCs and PTs by initial study treatment received at Core baseline. The SOCs will be presented in alphabetical order and PTs will be ordered within the SOC by decreasing proportion in the ranibizumab 0.2 mg treatment arm (with/without laser.)). Patients who experienced multiple AEs for a preferred

term will be counted once, similarly for patients with multiple AEs per system organ class. In-text tables will display the frequency of AEs at the PT level. Post-text table will commonly display the frequency of AEs at the PT levels within the relevant SOC.

Only treatment-emergent AEs will be summarized, separately for ocular and non-ocular AEs (according to the investigator’s response on the AE CRF form).

Guidance of Data Entry rules in the Extension study eCRF which provides details on handling of Adverse Events (AEs) and Serious Adverse Events (SAEs) in Extension study.

- Adverse Events (AEs) and Serious Adverse Events (SAEs) ongoing at the end of Core study visit which are ongoing at the Extension study informed consent form date needs to be reported as Adverse Event (AEs) or Serious Adverse Events (SAEs) for Extension study. Adverse event term, preferred term, category, does Adverse event meet definition of Serious Adverse events, Serious adverse event date, severity, location, laterality, Adverse Event start date and time must match between Core and Extension study.

Note: there can be differences across seriousness criteria, action taken with study treatment, medication or therapies taken etc.

- AEs which resolved in the Core study should not be re-entered (duplicated) in the Extension.

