- The absence of active ROP at 52 weeks from the baseline visit of the Core study as defined in [Section 2.8.1](#)
- The recurrence of ROP up to 40 weeks from the baseline visit of the Core study
- The absence of active ROP, and individual components of active ROP at 40 weeks from the baseline visit of the Core study

[REDACTED]

- Patient's physical development (standing/sitting height, leg length, weight and head circumference)
- The patient's health status (respiratory function, hearing function, duration of hospitalization from birth to first hospital discharge home, and weight at discharge)
- The type, frequency, and severity of ocular and non-ocular adverse events including AEs, SAEs, AEs by maximum severity
- The type, frequency, and severity of ocular and non-ocular adverse events with onset date on/after extension baseline, including AEs, SAEs, AEs by maximum severity

[REDACTED]

- Demographics (including sex, geographical region, gestational age at birth, gestational age at birth by category) and ROP disease status by subject at core baseline will be presented descriptively.
- Summary of the safety follow-up period since Core study baseline

- Summary of body height, body weight, and head circumference at Core study baseline, at the year 2 visit of the Extension study, and their change from Core study baseline to the year 2 visit
- Subject disposition
- Summary of reasons for permanent discontinuation from study treatment
- Deaths by preferred term
- Number (%) of subjects with deaths, SAEs or AEs leading to permanent discontinuation of study treatment
- Analysis sets by treatment
- Pre-retinal fibrosis and its relationship to laser therapy, ocular injection therapy, and study drug by eye

The safety follow up period (in months) is defined as: (The earlier date of the extension EOS data and snapshot date of the interim analysis – Core study baseline date +1)/30.

In addition, a selection of the above outputs will be repeated for the subgroup of Japan, to support the submission to the PMDA.

3 Sample size calculation

The sample size calculation is not based on a power calculation. The number of patients enrolled in this study depends on the number of patients that were enrolled and completed the Core study, are willing to participate in the Extension study and fulfill the eligibility criteria of the Extension study ([Section 4](#) of Protocol).

4 Appendix

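### Adverse events that start between the last Core visit and Extension baseline are filed as medical history, so AE summaries declared from first Core treatment can under-count them; the interim II follow-up formula still counts that gap

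*SAP*

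**What the plan says.** Section 2.9 splits the safety observation period into segment a (first Core treatment to last Core visit) and segment c (Extension baseline to last Extension visit). If the two visits are not on the same day, a segment b lies between them, and safety signs arising there "will be reported as medical history of Extension baseline".

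Section 2.4 gives the data-entry rule for AEs and SAEs. Those "which started after end of Core study and resolved before the time of Extension study enrollment (Baseline Visit) will be reported as Extension medical history", marked as not ongoing. Those that start in the gap and "are ongoing at the time of Extension study enrollment (Baseline Visit) will be reported as Extension medical history" are marked as ongoing.

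The declared safety window has no such break. Table 1-1 runs the AE objective "from the first study treatment in the Core study up to V203 (Week 40" and on to V302 and V399. Section 2.9.2, referring to Core treatment, states: "Adverse events will be deemed treatment emergent if the AE start time is on or after the time of dose of the first study treatment". Section 2.9.1 summarizes the risk-management-plan events over the whole study.

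Follow-up time is defined twice. For non-seamless children, Section 2.9 adds segments a and c. Section 2.15, under the words "The safety follow up period (in months) is defined as", takes the earlier of the Extension end-of-study and snapshot dates, subtracts the Core baseline date, adds one day and converts to months. It does not subtract segment b.

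**The concern.** The AE tables in Section 2.9.2 are built from AE records. An SAE that starts in segment b meets the treatment-emergent definition and lies inside the Table 1-1 window, but the entry rule gives it a medical-history record instead. It can then be absent from the all-AE table, the SAE table, the risk-management-plan summary and the count of SAE hospitalizations. It can also be absent from the table of AEs starting before Extension baseline, although its start date qualifies.

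These are preterm infants a few months after treatment, and safety is a secondary objective tied to the paediatric investigation plan. A known, dated event would be presented as background rather than outcome. At interim II, the stated follow-up would also include time that Section 2.9 treats as unobserved.

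**Working it through.** **Which table receives which event (non-seamless child)**

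| Event | Filed as | In the AE tables? |
|---|---|---|
| Starts in Core, ends in Core or in the gap | Core AE record (plus a history entry if it ends in the gap) | Yes |
| Starts and ends in the gap | Extension medical history, not ongoing | No |
| Starts in the gap, ongoing at Extension baseline | Extension medical history, ongoing | No |
| Starts on or after Extension baseline | Extension AE | Yes |

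Only the two middle rows are affected. Section 2.4 does tabulate segment-b history by system organ class and preferred term, with ocular and non-ocular shown separately, so these events change table rather than vanish. That table is not specified by severity, seriousness or relationship.

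**Boundary date.** Section 2.9.2 requires SAEs that newly occur after Extension consent to be reported as part of the Extension study. Section 2.4 sends SAEs that start after Core to history up to the baseline visit. If consent precedes Visit 201, an SAE between the two dates falls under both rules.

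**Follow-up time.** The plan gives no worked figure to reproduce, so I put the same dates into both formulas. Assumptions: first treatment and Core baseline on day 0, last Core visit on day 168 (24 × 7), end of follow-up on day L, Extension baseline g days after the last Core visit.

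- Section 2.9, non-seamless: (L − (168 + g) + 1) + (168 − 0 + 1) = L − g + 2
- Section 2.15, in days: L − 0 + 1 = L + 1
- Difference: (L + 1) − (L − g + 2) = g − 1 days

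| L | g | Section 2.9 | Section 2.15 | Excess |
|---|---|---|---|---|
| 730 | 30 | 702 | 731 | 29 days (4.1%) |
| 730 | 60 | 672 | 731 | 59 days (8.8%) |
| 730 | 90 | 642 | 731 | 89 days (13.9%) |
| 1095 | 30 | 1067 | 1096 | 29 days (2.7%) |
| 1095 | 60 | 1037 | 1096 | 59 days (5.7%) |
| 1095 | 90 | 1007 | 1096 | 89 days (8.8%) |

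Seamless check: (730 − 168) + (168 − 0 + 1) = 562 + 169 = 731, equal to 730 − 0 + 1. The two definitions agree when there is no gap.

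**Illustration of under-counting.** Assume a constant first-event rate r per year over 731 days (T = 731/365.25 years). The proportion with at least one event is 1 − exp(−rT). When gap onsets are dropped, T falls by (g − 1)/365.25.

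| r | Continuous | g = 30 | g = 60 | g = 90 |
|---|---|---|---|---|
| 0.5 | 63.2% | 61.7% | 60.1% | 58.5% |
| 1 | 86.5% | 85.4% | 84.1% | 82.8% |

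These figures apply to a group in which every child has that gap. The SAP gives neither rates nor gaps.

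**The case against.** The gap handling is deliberate and disclosed: Section 2.9 names segment b, says where its events go, and gives separate formulas. Whether events between two studies are AEs or history is partly a data-collection decision that the protocol may govern. This stands as an explanation. It does not reconcile the rule with Table 1-1, Section 2.9.1 or the treatment-emergent definition, none of which mentions the exclusion.

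Several stronger readings are tempting, but the documents do not support them:

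- A reader might infer that incidence is biased downward for every non-seamless child. Section 2.9.2 counts a patient once per preferred term in a crude incidence, so a child's status changes only if the sole qualifying event for that row started in the gap.
- A reader might infer that the arm comparison is distorted. Nothing shows that gaps differ by arm.
- A reader might take the share of calendar time as the size of the bias. An assumed 28-day gap is 25% of the 112 days between weeks 24 and 40 (28/112), but about 1.5% of five years (28/1826). Neither is a share of events.
- A reader might see the Appendix 4.1.2 matrix, which can place AE starts between the last Core visit and Extension baseline, as a flat contradiction. If consent precedes Visit 201, such AE records can legitimately exist.
- A reader might extend the point to procedures, since Section 2.5.3 also sends gap procedures to history. That section displays procedures separately for Core and Extension and declares no continuous display from which they would be missing.
- A reader might think that the interim II formula biases AE rates. The AE tables use crude incidence, and no stated rate has this period as its denominator.

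**Conclusion.** The point holds in limited form. The filing rule and the declared AE window disagree, and following the plan as written can under-count gap-onset AEs and SAEs in the treatment-emergent, risk-management-plan and SAE-hospitalization summaries. These events are misclassified, not erased. Seamless children and Core-onset events are unaffected. The size cannot be determined from the SAP, and the incidence figures above are illustrations only.

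The two follow-up definitions differ by exactly the roll-over interval minus one day, provided that Core baseline is the day of first treatment and both use the same end date. This overstates the reported observation time at interim II and nothing beyond that. The consent and baseline-visit boundaries for SAEs also need reconciling. The study is descriptive and has no type I error control, so the change is one that should be made; it does not invalidate the analysis.

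**What to change.** 1. In Section 2.9.2, add a supplementary treatment-emergent table, and a matching risk-management-plan table, that includes Extension medical-history records with onset after the last Core visit and before Visit 201, flagged as gap-onset. Leave out history entries that duplicate a Core AE.
2. For partial onset dates of these records, apply the floor of last Core visit plus one day used in the Appendix 4.1.2 AE matrix. The Appendix 4.1.3 rule for conditions ongoing at Extension baseline has no such floor and could move a gap onset back into Core.
3. Include these records in the SAE and hospitalization summaries only where seriousness is recorded; otherwise list them.
4. State in Table 1-1 and Section 2.9.2 that the main AE tables cover segments a and c only.
5. Use the Section 2.9 two-segment definition for the interim II follow-up period, keeping the interim's own end date.
6. Choose one boundary, consent or baseline visit, for SAEs in Sections 2.4 and 2.9.2. Correct the cross-reference in Section 2.9, which cites Section 2.3 for history rules that stand in Section 2.4.

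The cost is SAP wording, one derivation from records already collected, and a few extra tables. The limitation is that gap records may lack severity, causality and seriousness, so not every AE summary can be repeated with them.

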2.9.1 Risk Management Plan (RMP) adverse events

The number and percentage of patients who report adverse events (AEs) as safety risks (based on selected preferred terms) by the current version of the Risk Management Plan (RMP) at the time of database lock, will be summarized by risk categories for ocular and systemic safety risks for the entire study period. In addition, the analysis will include number and percentage of patients with each of the preferred terms that define each of the safety risk categories. Detailed specifications to identify which MedDRA preferred terms belong to which risk category will be added later – based on the valid RMP at that time-point.

A listing for AEs of safety risk by preferred term will also be produced.

2.9.2 Adverse events (AEs)

As a default, no summary tables for AEs that occur prior to the first study treatment in either eye will be produced.

Adverse events that occur prior to the first study treatment in either eye in Core study will be listed for patients.

Adverse events will be deemed treatment emergent if the AE start time is on or after the time of dose of the first study treatment in the Core study. When an AE's start date is equal to the date of first study treatment and either the start time of the AE or the first treatment time is missing, AEs are defined as treatment emergent. As stated in [Appendix 4](#), adverse events with completely missing start date will be defined as treatment emergent.

The AE incidence rates will be tabulated using the latest MedDRA SOCs and PTs by initial study treatment received at Core baseline. The SOCs will be presented in alphabetical order and PTs will be ordered within the SOC by decreasing proportion in the ranibizumab 0.2 mg treatment arm (with/without laser.)). Patients who experienced multiple AEs for a preferred

term will be counted once, similarly for patients with multiple AEs per system organ class. In-text tables will display the frequency of AEs at the PT level. Post-text table will commonly display the frequency of AEs at the PT levels within the relevant SOC.

Only treatment-emergent AEs will be summarized, separately for ocular and non-ocular AEs (according to the investigator’s response on the AE CRF form).

Guidance of Data Entry rules in the Extension study eCRF which provides details on handling of Adverse Events (AEs) and Serious Adverse Events (SAEs) in Extension study.

- Adverse Events (AEs) and Serious Adverse Events (SAEs) ongoing at the end of Core study visit which are ongoing at the Extension study informed consent form date needs to be reported as Adverse Event (AEs) or Serious Adverse Events (SAEs) for Extension study. Adverse event term, preferred term, category, does Adverse event meet definition of Serious Adverse events, Serious adverse event date, severity, location, laterality, Adverse Event start date and time must match between Core and Extension study.

Note: there can be differences across seriousness criteria, action taken with study treatment, medication or therapies taken etc.

- AEs which resolved in the Core study should not be re-entered (duplicated) in the Extension.
- An Extension adverse event or serious adverse events with a start date prior to end of Core study must have a corresponding Core adverse event record.
- Any serious adverse events, regardless of causality, newly occurring or recurring after Informed Consent Form was obtained for the Extension study needs to be reported to Novartis Safety as part of the Extension study.
- Serious adverse events should never be reported to Novartis Safety in duplicate, i.e. for the Core and the Extension study. Any serious adverse events follow-ups sent to Novartis Safety should be sent as part of the study where the original SAE was reported.

Item	Started	Ended	Action for ECRF
(S)AEs	Core	Ongoing end of Core and ongoing at beginning of Ext (Signed ICF)	Record as (S)AE in Extension
(S)AEs	Ext		Record as (S)AE in Extension

All AE tables will show the frequency and crude incidence rate by initial study treatment received and total. The following AE tables will be produced for ocular and non-ocular AEs separately.

- All adverse events regardless of study treatment or procedure relationship
- Adverse events with start dates prior to the extension baseline
- Adverse events with start dates on or after the extension baseline
- Serious adverse event, regardless of study treatment or procedure relationship
- All adverse events suspected to be related to study treatment or procedure
- Serious adverse event suspected to be related to study treatment or procedure

- All adverse events causing permanent study treatment discontinuation
- All adverse events causing permanent study discontinuation
- All adverse events by maximum severity (mild, moderate, severe)

In addition, the following summaries will be produced.

- Deaths, SAE, or AE leading to permanent study treatment discontinuation

All deaths, SAEs, and AEs leading to permanent study drug discontinuation will be listed separately.

For missing dates for medication or AE, please refer to [Appendix 4](#) for imputation rule.

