1.1 Study design

This is a multicenter open-label Extension study ([Figure 1-1](#)). Patients who have successfully completed the 24-week Core study (CRFB002H2301) are eligible for entry into the study. Visit 201/ baseline visit of the Extension study can occur on the same day as the last visit in the CRFB002H2301 study.

At Visit 201 (Extension baseline), the investigator or his/her delegate will contact the IRT after confirming the patient fulfills all the inclusion/exclusion criteria. Sample size estimation or formal power calculation was not done for this study. The number of patients is the actual enrollment in the Extension study (Section 4 of study protocol).

Treatment with study ranibizumab (either as re-treatment after ranibizumab has already been injected or as switch ranibizumab treatment from study laser therapy administered in the Core study) will be permitted for eligible eyes up to and including the study visit V203 (week 40 from the baseline visit in the Core study (CRFB002H2301) (equal to week 16 from the baseline visit in Extension study, when the baseline visit in Extension study coincides with the week 24 visit in the Core study) [Epoch 1]). During Epoch 1, the investigator or his/her delegate will contact the IRT upon decision to administer study treatment. IRT will specify a unique medication number for the package of study drug to be dispensed to the patient. The remainder of the Extension study (from the study visit V203, to patients' 5th birthday visit) [Epoch 2] is observational.

[figure not shown]
Assessment visits will be performed regularly throughout Epoch 1 and Epoch 2, with the last study visit to be as close as possible to the patient's fifth birthday. The assessments related to the primary objective will be performed at the study visit V399, corresponding to the approximate time of the patient's fifth birthday.

Two interim analyses are planned for the study. Additional interim analyses may be conducted on safety or efficacy data as required.

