2.2.1.2 The last study visit

The last study visit is Visit 399 (including premature withdrawal). If the patient does not discontinue the study, Visit 399 will occur close to the patient's fifth birthday.

For the visual acuity at Visit 399, the study day will be allocated to the 5th birthday visit if the study day is before the 5th birthday and within 3 months of the 5th birthday, or if the study day is after the 5th birthday.

For all other variables except for the visual acuity, the study day for the premature withdrawal Visit 399 will be allocated to the nearest planned main visit if data for the nearest planned main visit does not already exist and if the study day is within the allocation windows of the planned main visit.

All applicable assessments will be captured by scheduled visit. [Table 2-2](#) shows the allocation windows of premature withdrawal visit to a scheduled main visit of H2301E1.

Table 2-2 Allocation of premature withdrawal visit

Scheduled main visit number	Scheduled visit study week/year	Scheduled visit window in days
202	Week 32	197 – 253
203	Week 40	254 – 323
301	Week 52	324 – (Start date of mother's last menstrual period – Core study baseline visit date+766)
302	2-year corrected age	(Start date of mother's last menstrual period – Core study baseline visit date+891) – (Start date of mother's last menstrual period – Core study baseline visit date+1131)
303	3-year corrected age	(Start date of mother's last menstrual period – Core study baseline visit date+1257) – (Start date of mother's last menstrual period – Core study baseline visit date+1497)
304	4 th birthday	(Start date of mother's last menstrual period + gestational age (in weeks) *7 – Core study baseline visit date +1341) – (Start date of mother's last menstrual period + gestational age (in weeks) *7 – Core study baseline visit date +1581)
	5 th birthday	For visual acuity: (Start date of mother's last menstrual period + gestational age (in weeks) *7 – Core study baseline visit date +1736) – End of study For variables other than visual acuity: (Start date of mother's last menstrual period + gestational age (in weeks) *7 – Core study baseline visit date +1706) – (Start date of mother's last menstrual period + gestational age (in weeks) *7 – Core study baseline visit date +1946)

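### Adverse event tables give only crude percentages over follow-up of up to about five years; adding first-event rates per child-year would guard them against unequal withdrawal

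*SAP*

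**What the plan says.** SAP section 2.9.2 sets one measure for the adverse event tables: "All AE tables will show the frequency and crude incidence rate by initial study treatment received and total". The same section counts a child with several events under one preferred term or system organ class once, so the measure is a proportion of children. Section 2.9.1 does likewise for the Risk Management Plan (RMP) risks: "The number and percentage of patients who report adverse events (AEs) as safety risks".

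Two of the tables in section 2.9.2 split events by onset: "Adverse events with start dates prior to the extension baseline" and "Adverse events with start dates on or after the extension baseline".

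On follow-up:
- Section 1.1 fixes the first period: "Patients who have successfully completed the 24-week Core study (CRFB002H2301) are eligible for entry into the study". It places the end of the second near the fifth birthday, "with the last study visit to be as close as possible to the" day itself.
- Section 2.2.1.2 uses Visit 399 both as the planned final visit and as the premature withdrawal visit.
- Section 1.3 takes adverse events at Interim Analysis II up to a calendar cut-off rather than to a visit.
- Section 2.9 derives observation time for each child: "The safety observation period (days) for treated patients comprises two segments", namely segment a in the Core study and segment c in the Extension. The gap between them, segment b, is left out.
- Section 2.5.1 displays the duration of observation by arm, and section 2.15 adds a follow-up summary at Interim Analysis II.

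No visible text uses the section 2.9 observation time as a denominator for an adverse event table.

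**The concern.** A crude percentage depends on how long children are watched as well as on how often events occur. Children who withdraw stay in the denominator, while events after they leave go unseen. If one arm loses more children, its percentage falls for that reason alone and the arm looks safer. At Interim Analysis II, children enrolled earlier also contribute more adverse event time than those enrolled later.

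The two tables split at Extension baseline cover very different lengths of time. A reader who sets them side by side to ask whether events became more or less frequent would mostly be reading the length of each period.

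Adverse events are the first-listed secondary objective in Table 1-1, reported up to the fifth birthday. The Extension exists largely to supply this long-term evidence.

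**Working it through.** The SAP states no event rate, withdrawal rate or sample size, so it has no figure to reproduce. The calculations below show the mechanism. Age at Core baseline, event risks and drop-out are assumptions.

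**1. Length of the two periods**

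Inputs: Core study 24 weeks = 168 days (section 1.1); fifth birthday at day 1826 of life (5 × 365.25, rounded); roll-over on the same day; age at Core baseline assumed to be 8 to 16 weeks, with 0 as the outer bound.

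Extension days = 1826 − age at Core baseline − 168. Ratio = Extension days / 168.

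With one unchanged hazard, a crude incidence p over 24 weeks becomes 1 − (1 − p)^ratio in the later table, for children followed to the end:

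| Age at Core baseline | Extension days | Ratio | p = 2% | p = 5% | p = 10% | p = 20% |
|---|---|---|---|---|---|---|
| 0 (bound) | 1658 | 9.87 | 18.1% | 39.7% | 64.6% | 88.9% |
| 8 weeks | 1602 | 9.54 | 17.5% | 38.7% | 63.4% | 88.1% |
| 12 weeks | 1574 | 9.37 | 17.2% | 38.2% | 62.7% | 87.6% |
| 16 weeks | 1546 | 9.20 | 17.0% | 37.6% | 62.1% | 87.2% |

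So 10% in the first table would sit beside about 62% to 63% in the second with no change in event frequency.

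**2. Two arms with the same hazard but different withdrawal**

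Inputs: age at Core baseline 12 weeks (84 days), so total follow-up T = 1826 − 84 = 1742 days. All children complete the 168 Core days. A fraction d withdraws evenly over the remaining 1574 days.

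Crude incidence = (1 − d)(1 − e^(−hT)) + d × mean of (1 − e^(−ht)) for t uniform on 168 to 1742.

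For a risk of 30% over full follow-up:
- h = −ln(0.70)/1742 = 0.3567/1742 = 0.0002048 per day.
- Mean of e^(−ht) among those who withdraw = (e^(−168h) − e^(−1742h)) / (1574h) = (0.9662 − 0.7000)/0.3223 = 0.826, so their observed risk is 17.4%.
- Crude incidence = 30.0% − d × 12.6 points.

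| Drop-out | Crude incidence | Apparent difference |
|---|---|---|
| 10% vs 10% | 28.7% vs 28.7% | 0 |
| 10% vs 20% | 28.7% vs 27.5% | 1.3 points |
| 10% vs 30% | 28.7% vs 26.2% | 2.5 points |
| 10% vs 40% | 28.7% vs 25.0% | 3.8 points |

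For the same three unequal contrasts, a full-follow-up risk of 10% gives differences of 0.4, 0.9 and 1.3 points; a risk of 50% gives 2.0, 3.9 and 5.9 points.

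**3. The same examples with person-time**

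Under a constant hazard, expected first events divided by expected time at risk equals h whatever the length of follow-up. In example 2, both arms have 0.0002048 × 365.25 × 100 = 7.5 per 100 child-years. In example 1 with p = 10%, both periods have −ln(0.90)/168 × 365.25 × 100 = 22.9 per 100 child-years. The rate ratio is 1.0 in each case.

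**The case against.** Much of the case for leaving the tables alone is sound.

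- **The measure fits the endpoint.** Table 1-1 gives the unit as the number and percentage of patients. A reader might infer that crude incidence contradicts the objective; it does not. Section 2.1 also disclaims formal inference, and no test on adverse events is planned.
- **Unequal follow-up between arms is not documented.** A reader might infer that the arms are known to differ. All children completed the same Core study and all arms are followed to the same age. A difference needs differential withdrawal, and the SAP gives no losses. The Interim Analysis II cut-off makes follow-up vary between children, not necessarily between arms.
- **The SAP never proposes comparing the two period tables.** Within each table the arms share the same planned window. The warning concerns how readers may use the pair, not a stated analysis.
- **Follow-up is not hidden.** Duration is displayed by arm (sections 2.5.1 and 2.15) and disposition by epoch (section 2.4.1), so a marked imbalance would be visible. Those displays do not give time to first event, however, so a reader could not work out the adjusted rate.
- **Deaths.** Keeping children who die in the denominator is correct for the proportion who experience an event. The difficulty lies with withdrawal.
- **The rate has its own weakness.** It assumes a roughly constant hazard, yet segment c joins Epoch 1, when ranibizumab may be given, to the observational Epoch 2.

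These points reduce the matter to an improvement. They do not remove the dependence of the crude percentage on follow-up.

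**Conclusion.** The point holds as a cheap improvement, not as an error in the plan. The adverse event tables show crude incidence alone, although the SAP already defines the observation time from which a rate could be built.

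The difference in period length follows from the design: roughly ninefold for completers, under the assumed ages and same-day roll-over. The two split tables therefore cannot be read against each other as event frequency. The bias between arms is conditional. It is about 1 to 4 points for drop-out of 10% versus 20% to 40% at a five-year risk of 30%, with equal constant hazards and even withdrawal. It is smaller for rarer events, larger for commoner ones, and near zero if drop-out is similar.

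The SAP does not support a claim that the planned comparison between arms is biased, only that it is unprotected if withdrawal turns out unequal.

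**What to change.** Keep every crude percentage. For any AE, any SAE, the RMP risk categories and the two Extension-baseline tables, add by arm the child-years at risk and the number of children with a first event per 100 child-years.

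- Count time to the first event in the category; otherwise censor at last visit, death or data cut-off.
- Use segment a time for the table of events before Extension baseline and segment c time for the table from Extension baseline onward, counting in each the first event with onset in that segment. Use a plus c for the whole study.
- Leave events dated in gap b out of both numerators, in line with section 2.9. This needs stating because the start-date imputation in section 4.1.2 can place an event after the last Core visit but before Extension baseline.
- Label the rates supplementary and descriptive. Note that any contrast between periods remains confounded with age and treatment opportunity.

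The cost is a paragraph of SAP text, extra columns in a few tables, and programming of time to first event for each category, since section 2.9 derives only total observation time. No new data are needed. The constant-hazard assumption is the main drawback, which is why the rate belongs beside the crude percentage and should not replace it.
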